5. GENERAL METHODOLOGY AND CONVENTIONS

The final analysis will be performed after dataset release.

5.1. Hypotheses and Decision Rules

The primary hypothesis to be tested is whether or not there is a difference in median time (days) to sustained alleviation of all targeted COVID-19 signs and symptoms through Day 28 between PF-07321332/ritonavir and placebo. The statistical hypothesis is as follows:

- *The null hypothesis (H₀) is that there is no difference in median time to sustained alleviation of targeted symptoms of COVID-19 between PF-07321332/ritonavir and placebo.*
- *The alternative hypothesis (H₁) is that there is a difference in median time to sustained alleviation of targeted symptoms of COVID-19 between PF-07321332/ritonavir and placebo.*

Because the prespecified 45% interim analysis of the primary endpoint was not met, the following secondary endpoints will be analyzed to provide a point estimate and 95% CI to measure associated variability. The analysis will be performed with a nominal alpha:

- 1) Proportion of participants with COVID-19-related hospitalization or death from any cause through Day 28.*
- 2) Number of COVID-19-related medical visits through Day 28.*

In support of the COVID-19 related medical visits endpoint, the number of days in hospital and ICU stay in patients with COVID-19-related hospitalization through Day 28 will be summarized.

Other secondary endpoints listed below will be subsequently tested following the Hochberg procedure.

- Time (days) to sustained resolution of all targeted signs/symptoms through Day 28 mITT1 population.
- Proportion of participants with a resting peripheral oxygen saturation $\geq 95\%$ at Days 1 and 5 mITT1 population.
- Proportion of participants with severe signs/symptoms attributed to COVID 19 through Day 28.

5.2. General Methods

All data will be presented by treatment groups. Descriptive statistics will be provided for efficacy endpoints. The following listing of individual participants data will also be produced: (Disposition Events, Potentially Important Protocol Deviations, Subject Evaluation Groups, Demographic Information, Primary Diagnosis, Concomitant Medications, Compliance with Study Intervention, primary efficacy endpoint [time to sustained alleviation of all targeted signs and symptoms through Day 28], and the two key secondary endpoints [proportion of participants with COVID-19-related hospitalization or death from any cause through Day 28; number of COVID-19-related medical visits through Day 28], Adverse Events, Laboratory Data – Standardized (all the variables that are listed in the SAP [Section 6.4](#) plus visit ID, participant ID, treatment).

The number of participants screened will be reported. The number of participants randomized to the double-blind treatment phase, completing the study drug administration, completing the study, completing the follow-up phase (through Day 34 visit) and discontinued the study will be summarized from the FAS analysis set for each treatment group.

Baseline demographic and other characteristics will be tabulated for the FAS and summarized by treatment group. Quantitative variables will be described by standard descriptive statistics (mean, standard deviation, median minimum, and maximum), and qualitative variables will be summarized by frequency tables with number and proportion in each category (with the corresponding sample sizes).

For mITT1 population, strata will be region, vaccination subgroup/strata, onset of signs and symptoms of COVID-19 (≤ 3 days, $>3-5$ days), nasopharyngeal (Y/N), and baseline viral load.

5.2.1. Analyses for Binary Endpoints

Binary endpoints other than COVID-19 related hospitalization and death due to any cause (ie, proportion of participants with severe signs/symptoms attributed to COVID-19 through Day 28, worsening status in 1 or more self-reported COVID-19 associated symptoms through Day 28 and proportion of participants with death [all cause] through Week 24) will be summarized with the number and percent of participants satisfying the endpoint. Treatment comparisons between groups will be presented as odds ratios with 95% confidence intervals and P-value based on logistic regression model (if data permits).

5.2.2. Analyses for Continuous Endpoints

For continuous endpoints (ie, viral titers measured via RT-PCR in nasal swabs over time), an MMRM analysis of covariance model will be used to analyze change from baseline over time. Estimated mean differences between treatments and their respective 95% CI and P-values will be calculated. In addition, an ANCOVA model will be used to analyze change from baseline (Day 1) to Day 5 in viral titers.

For mITT1 population, the strata will be region, vaccination subgroup/strata, baseline serology (positive or negative), and baseline viral load ($<10^4$ copies/mL, $\geq 10^4$ copies/mL).

5.2.3. Analyses for Categorical Endpoints

For categorical endpoints, (ie, proportion of participants with a resting peripheral oxygen saturation $\geq 95\%$ at Days 1 and 5), proportion of participants for each category will be summarized for each group and a test for homogeneity of odds ratio using Breslow-Day test will be summarized.

5.2.4. Analyses for Count Endpoints

For count endpoints (ie, number of COVID-19 related medical visits through Day 28 and number of days of hospitalizations/ICU stay in participant with COVID-19-related hospitalization through Day 28), a negative binomial regression model analysis, using the

log total number of days of data collection as the participant offset variable, will be conducted and the difference in estimated rate will be provided.

5.2.5. Analyses for Time-to-Event Endpoints

Time-to-event endpoints (ie, Time (days) to sustained resolution of all targeted signs/symptoms through Day 28) will be summarized with Kaplan-Meier curves. Log-rank test will be used to compare the time-to-event between the treatment group.

5.3. Methods to Manage Missing Data

For missing efficacy data other than time to event endpoints, last observation carried forward (LOCF) approach will be used. For efficacy endpoints related to COVID-19 sign/symptoms, missing data at baseline will be treated as mild.

For safety data, missing and partial dates will be programmatically handled according to Pfizer standards.

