- If the participant's last observed data is prior to Day 21, then impute as an event with event day as day of last observed data +1.
- If the participant's last observed data is on or after Day 21, then no imputation for event will be done and participant remains censored at day of last observed data.

6.2.4. Proportion of Participants with Death (all cause) through Week 24

Descriptive statistics will be used to summarize proportion of death through Week 24 by treatment group using mITT1 populations. Treatment comparisons between groups will be presented as odds ratios with 95% confidence intervals and P-value based on logistic regression model (if data permit).

If zero counts are observed in either treatment group, the Fishers Exact test will be performed (instead of logistic regression) and p-value provided.

The participants enrolled under or after protocol amendment 6 will not include this summary.

6.2.5. Number of COVID-19 Related Medical Visits through Day 28

The number of COVID-19 related medical visits will be analyzed with a negative binomial regression model, using the log total number of days of data collection as the participant offset variable (if data permit). The resulting analysis will evaluate the difference in estimated rate of number of medical visits between treatment groups and the associated 95% CI. The analyses will be done using mITT1 populations.

6.2.6. Number of Days of Hospital and ICU Stay in Participants with COVID-19 Related Hospitalization

Health resource utilization data will be summarized by treatment group for each treatment. The analyses will be done using mITT1 populations. Descriptive statistics (ie, mean, median, range) will be used to summarize this endpoint.

The resulting analysis will provide the estimated difference in the average of number of days stayed in the hospital between treatment groups, with p-value and 95% confidence interval. The analyses will be done using the mITT1 population.

6.2.7. Proportion of Participants with Severe Signs/symptoms Attributed to COVID19 through Day 28

Participants will record a daily severity rating of their symptom severity over the past 24 hours based on a 4-point scale in which 0 is reported if no symptoms were present; 1 if mild; 2 if moderate; and 3 if severe. A participant with severe score for any targeted symptoms post-baseline will be counted as severe.

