worsening will be assessed to include hospitalization due to COVID-19 and death of any cause. An expanded definition of worsening of signs and symptoms that will include CRF data (hospitalization due to COVID-19 and death of any cause) is defined as follows: Participant with hospitalization due COVID-19 or death of any cause will be considered as having worse signs and symptoms, this definition overrides the observed worsening of signs and symptoms from participant diary data. To incorporate hospitalization and death in the expanded worsening of signs and symptoms, date of hospitalization and date of discharge will be used.

To evaluate the progression to worsening of symptoms attributed to COVID-19, the following analysis will be performed for both worsening and expanded worsening and treatment comparison between groups will be done using the same statistical method as mentioned above:

- Proportion of participants with any progression to worsening of targeted symptoms attributed to COVID-19 Day 2 to Day 6 (during treatment).
- Proportion of participants with any progression to worsening of targeted symptoms attributed to COVID-19 Day 7 to Day 28 (post treatment).

6.2.11. Proportion of Participants with a Resting Peripheral Oxygen Saturation $\geq 95\%$ at Days 1 and 5

The oxygen saturation level will be measured for each participant. A resting peripheral oxygen saturation will be derived programmatically based on following table:

Oxygen saturation (Yes/No)	
$\geq 95\%$	Yes
$< 95\%$	No

The count and proportion of participants with a resting peripheral oxygen saturation $\geq 95\%$ will be summarized by treatment group and by visits (Days 1 and 5). A cross tabulation will be presented for both Day 1 and Day 5, ie, for each proportion presented at Day 1, both proportions at Day 5 will be summarized. Treatment comparison between group for the odds ratio (baseline (Day 1) $\geq 95\%$ vs $< 95\%$) of comparing oxygen saturation $\geq 95\%$ at Day 5 will be analyzed with a Breslow-Day test for homogeneity of the odds ratios. The analyses will be done using mITT1 populations. Missing data at Day 1 or Day 5 will be excluded from the analysis.

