6.2.13. Viral Titers (quantitative RT-PCR) Measured in Nasal Swabs Over Time

The viral load data measured at Day 1 and Day 5 are nasopharyngeal samples. These are the samples that were used on the POC analysis. POC analysis of viral load data occurred when 25% (approximately 200 participants in the primary analysis set with evaluable data) in the mITT1 population with evaluable data complete the Day 5 assessments.

Descriptive statistics by treatment group for the change from baseline will be provided. An analysis of covariance (ANCOVA) model will be used to analyze the change from baseline in log base10 transformed viral load (copies/mL) data. The ANCOVA model will include treatment group, baseline viral load, baseline serology, geographical region and vaccination status. Symptom onset to first dose date (≤ 3 days, > 3 days) will be used in the model dependent of population. Participants are excluded from the analysis for reasons of Not Detected, Zero or Missing baseline viral load result. Results from samples collected at non-nasopharyngeal site (like nostril, other or missing) are also excluded, as well as exclusions due to non-validated swab use (only viral load data based on samples collected through validated swab will be used for analyses).

The viral load measured in nasal or nasopharyngeal samples over time will be evaluated. The change from baseline to each visit (Day 3, Day 5, Day 10, Day 14) in viral load will be analyzed using an MMRM method. Viral load, including change from baseline, will be summarized by treatment group. Change from baseline to Day 3/Day 5/Day 10/Day 14 in viral load in the log base 10 scale will be statistically analyzed using a linear mixed-effect model. The model will contain log base 10 transformed baseline as a covariate, baseline serology status, treatment, day, treatment-by-day as fixed effects. Symptom onset to first dose date (≤ 3 days, > 3 days), nasopharyngeal (Y/N) will be used in the model as described in Section 3.4 and 3.5, dependent of population. The LS means and treatment difference will be calculated and presented with their corresponding 95% CIs. The analyses will be done using mITT1 populations.

CCI [REDACTED]

CCI [REDACTED]

CCI [REDACTED]

CCI [REDACTED]

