Proportion of participants with COVID-19 related hospitalization or death from any cause through Day 28	Sensitivity analysis for key secondary endpoint	mITT1	If the participant's last observed data is prior to Day 21, then impute as an event with event day as day of last observed data +1. If the participant's last observed data is on or after Day 21, do not impute an event and	Kaplan-Meier method

Endpoint	Analysis Type	Population	Data Inclusion and Rules for Handling Intercurrent Events and Missing Data	Analysis Model
			participant remains censored at day of last observed data.	
Proportion of participants with COVID-19 related hospitalization or death from any cause through Day 28	Sensitivity analysis for key secondary efficacy analysis for multiple enrollers	mITT1 including only data with first randomization within the study	All data collected will be included regardless of intercurrent events. Kaplan-Meier method to take account of losses to follow-up.	Kaplan-Meier method
Proportion of participants with COVID-19 related hospitalization or death from any cause through Day 28 by vaccination status	Subgroup analysis for key secondary endpoint	mITT1	Subset analysis identified in Section 6.4.	Kaplan-Meier method
Proportion of participants with COVID-19 related hospitalization or death from any cause through Day 28	Supplemental analysis for key secondary efficacy endpoint	PP	Participants who discontinued the study before Day 28 without event will be censored at Day 25.	Kaplan-Meier & Log rank test
Proportion of participants with death (all cause) through Week 24.	Secondary analysis	mITT1	All data collected will be included regardless of intercurrent events exclude participants enrolled under PA6	Logistic Regression
Number of COVID-19 related medical visits through Day 28.	Secondary analysis	mITT1	All data collected will be included regardless of intercurrent events. Missing data will not be imputed.	Descriptive statistics (based on negative Binomial Model)
Number of days in hospital and ICU stay in participants with COVID-19 related hospitalization through Day 28.	Secondary analysis	mITT1	All data collected will be included regardless of intercurrent events. Missing data will not be imputed.	Descriptive statistics
Proportion of participants with severe signs/symptoms attributed to COVID-19 through Day 28.	Secondary Efficacy Analysis	mITT1	All data collected will be included regardless of intercurrent events, LOCF for missing data.	Logistic regression model

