Progression to a expanded worsening status in 1 or more self-reported COVID19 associated symptoms through Day 28.	Secondary analysis	mITT1	All data collected will be included regardless of intercurrent events. Missing severity at baseline will be treated as mild.	Logistic regression model
Proportion of participants with a resting peripheral oxygen saturation $\geq 95\%$ at Days 1 and 5.	Secondary analysis	mITT1	All data collected will be included regardless of intercurrent events. Missing data will not be imputed.	Breslow-Day test for Homogeneity of the Odds Ratios
Viral titers measured via RT-PCR in nasal swabs over time.	Secondary analysis	mITT1	All data collected will be included regardless of intercurrent events. If visit data in viral load is missing, the earliest measurement	MMRM analysis

Endpoint	Analysis Type	Population	Data Inclusion and Rules for Handling Intercurrent Events and Missing Data	Analysis Model
			closest to the visit will be used for the visit.	
Viral titers measured via RTPCR in nasopharyngeal samples at Day 1 and Day 5.	Sensitivity analysis (POC)	mITT1	All data collected will be included regardless of intercurrent events. Use baseline viral load (continuous).	ANCOVA analysis
CCI [REDACTED]	CCI [REDACTED]	CCI [REDACTED]	CCI [REDACTED]	CCI [REDACTED]

* All: Combining mITT1 population from before and after Protocol Amendment #6, dated 09 Jun 2022.

Pre-PA5: mITT1 population from before Protocol Amendment #5, dated 21 Jan 2022,

Post-PA5: mITT1 population from after Protocol Amendment #5, dated 21 Jan 2022

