Appendix 2. Data Derivation Details

Appendix 2.1. Definition and Use of Visit Windows in Reporting

The following table defines the visit windows and labels to be used for reporting:

Visit Number	Visit Label	Definition [Day window]
2	Baseline	= Day -2 to Day 1
3	Day 3	= Day 3, with a window of ± 1 Day, (ie, Days 2 to 4)
4	Day 5	= Day 5, with a window of ± 1 Day, (ie, Days 4 to 6)
5	Day 10	= Day 10, with a window from Days 7 to 11
6	Day 14	= Day 14, with a window from Days 12 to 17
7	Day 21	= Day 21, with a window from 18 to 24
8	Day 34	= Day 34, with a window from days 25 to 37
9	Week 12	= Day 84, with a window of ± 7 Days, (ie, Days 77 to 91)
10	Week 24	= day 168 with a window of ± 7 days, (ie, Days 161 to 175)

- Viral Load: Baseline visit is set up according to study days of Day -2 to Day 1. The only viral load results collected after the start of dosing during the Baseline visit that are treated as Baseline data are those that were collected within 1 hour post start of dosing.
- Labs, COVID-19 Signs and Symptoms, Vital Signs: Baseline window will be Day -2 to Day 1, without any consideration to the time factor.
- When data from study Day 4 has an overlap between Day 3 and Day 5 windows, decision made is to assign the window according to the nominal visit. The rule will not be applicable to other study days 2 and 3 for Day 3 window, and days 5 and 6 for Day 5 window.
- If multiple readings fall into the same window, choose the one closer to the target day. If equidistant, then select the later one after the target day. If multiple observations fall on the same day after the windowing logic has been applied, average observations.

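### SAP 5.3's blanket LOCF rule contradicts the endpoint-specific missing-data rules and, with Appendix 1, puts substituted values in front of a viral-load MMRM that needs none

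*SAP*

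**What the plan says.** SAP 5.3, the general missing-data section, states: "For missing efficacy data other than time to event endpoints, last observation carried forward (LOCF) approach will be used". It makes no exception for endpoints that have their own rule. The protocol does not settle the matter, because section 9.1 leaves imputation rules to the SAP.

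The endpoint-level text differs:

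- **Oxygen saturation.** SAP 6.2.11: "Missing data at Day 1 or Day 5 will be excluded from the analysis". Its Appendix 1 row: "All data collected will be included regardless of intercurrent events. Missing data will not be imputed".
- **Medical visits and hospital/ICU days.** The Appendix 1 rows again say "Missing data will not be imputed". SAP 6.2.5 deals with incomplete follow-up in the medical-visits model through an offset for days of data collection.
- **Viral load.** SAP 6.2.13: "The change from baseline to each visit (Day 3, Day 5, Day 10, Day 14) in viral load will be analyzed using an MMRM method". The Appendix 1 row for that analysis begins "If visit data in viral load is missing, the earliest measurement" and goes on to use the one closest to the visit. The Appendix 1 row for the Day 5 ANCOVA gives no rule for a missing post-baseline value. The missing-value exclusion in 6.2.13 concerns baseline only.
- **Severe signs/symptoms.** Appendix 1 specifies LOCF, in agreement with 5.3, both for the through-Day-28 endpoint and for the Day 2 to 6 and Day 7 to 28 windows.

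**The concern.** Two programmers could each follow this SAP and report different results for the same endpoint. Under 5.3, a participant with no Day 5 saturation takes the Day 1 category at Day 5. Under 6.2.11 the same participant is dropped. Saturation and severe symptoms are two of the three endpoints that SAP 5.1 lists for Hochberg testing. Medical visits are one of the two endpoints for which 5.1 promises a point estimate and 95% CI.

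For viral load the issue goes beyond inconsistency. Both 5.3 and Appendix 1 substitute a value from another time before a model that can use the observed visits as they are. On a falling curve, an earlier value is too high for the later visit. The carried value may also be a different specimen type. The Schedule of Activities allows a nasopharyngeal swab in person and a self-collected nasal swab otherwise, and Day 10 is normally a telemedicine visit.

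For the windowed any-severe analyses, LOCF can place a severe score in a window in which the participant reported nothing.

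**Working it through.** **1. Text side by side**

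| Endpoint | SAP 5.3 | Endpoint-specific text | Agree? |
|---|---|---|---|
| Oxygen saturation, Days 1 and 5 | LOCF | Excluded (6.2.11); not imputed (Appendix 1) | No |
| Medical visits | LOCF | Not imputed (Appendix 1); offset (6.2.5) | No |
| Hospital/ICU days | LOCF | Not imputed (Appendix 1) | No |
| Viral load over time | LOCF | MMRM (6.2.13); fill from a nearby measurement (Appendix 1) | No |
| Viral load, Day 5 ANCOVA | LOCF | No post-baseline rule | 5.3 is the only rule |
| Severe signs/symptoms | LOCF | LOCF (Appendix 1) | Yes |

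Saturation needs no arithmetic. The analysis in 6.2.11 cross-tabulates Day 5 by Day 1 category, and LOCF puts every participant with a missing Day 5 value in the same category at both visits.

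**2. Viral load under LOCF**

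The plan states no figure to reproduce. The inputs are:

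- Assumed placebo mean log10 load at Days 1, 3, 5, 10 and 14: 6.5, 5.0, 4.0, 2.5, 1.8.
- Assumed true differences (active minus placebo): 0, -0.4, -0.8, -0.5, -0.2.
- Proportion missing, m: 5% and 18%, borrowed from the two study-discontinuation assumptions in protocol 9.5, and an assumed 10% between them. Missingness is taken as completely at random and equal in the arms.

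With true difference D(t) at the visit and D(last) at the last observed visit:

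- LOCF difference = (1 - m) × D(t) + m × D(last)
- Upward shift of an arm's mean = m × (mean at last visit - mean at visit t)

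For m = 10%:

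- Day 5, last seen Day 3: 0.9 × (-0.80) + 0.1 × (-0.40) = -0.76
- Day 5, last seen Day 1: 0.9 × (-0.80) + 0.1 × 0 = -0.72
- Day 10, last seen Day 5: 0.9 × (-0.50) + 0.1 × (-0.80) = -0.53
- Day 14, last seen Day 5: 0.9 × (-0.20) + 0.1 × (-0.80) = -0.26

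| Visit (last seen) | True | m = 5% | m = 10% | m = 18% | Direction |
|---|---|---|---|---|---|
| Day 5 (Day 3) | -0.80 | -0.78 | -0.76 | -0.73 | toward null |
| Day 5 (Day 1) | -0.80 | -0.76 | -0.72 | -0.66 | toward null |
| Day 14 (Day 5) | -0.20 | -0.23 | -0.26 | -0.31 | away from null |

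The placebo mean at Day 14 (last seen Day 5) is too high by m × (4.0 - 1.8) = m × 2.2. That is 0.11, 0.22 and 0.40 log10 for the three values of m.

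If the true difference is the same at both visits and missingness is equal, the bias in the difference is m × 0 = 0. If there is no treatment effect but 5% are missing on active and 18% on placebo, the Day 14 difference becomes (0.05 - 0.18) × 2.2 = -0.29. Swapping the arms gives +0.29.

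The Appendix 1 fill rule was not modelled. Its effect depends on whether the chosen measurement falls before or after the missing visit.

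**3. Any-severe analyses**

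Under SAP 6.2.7 one severe post-baseline score already makes a participant a case through Day 28, so carrying that score forward adds no case there. The windows behave differently. A participant whose last diary entry is severe on Day 6 becomes severe in Days 7 to 28 without any data in that window. The mITT1 set in SAP 4 requires only one dose, so a severe baseline score could also be carried into post-baseline days.

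**The case against.** The strongest reply is that 5.3 is a general convention and Appendix 1 has a column of missing-data rules for each endpoint. On the usual reading that the specific rule governs, saturation and counts are never imputed, LOCF is confined to the severe-symptom rows, and the over-time viral-load analysis follows its own rule. This is a sensible reading and probably the intended one. It is not written down, however, and it leaves LOCF as the only stated rule for the Day 5 ANCOVA. It also leaves the Appendix 1 fill in front of the MMRM.

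The impact is also limited. The primary and hospitalization/death endpoints use Kaplan-Meier methods and fall outside the LOCF sentence. Viral load has a descriptive objective and is not in the Hochberg list. SAP 2 makes all further p-values nominal. All of this stands.

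Four stronger readings are tempting and are not supported:

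- **That LOCF exaggerates the viral-load benefit.** The sign is not fixed: on the same assumed curve Day 5 moves toward the null and Day 14 away from it. Quoting Day 14 as a percentage of an assumed -0.20 would mislead.
- **That Appendix 1 contradicts the visit-window rule.** The tie-break in Appendix 2.1, "If equidistant, then select the later one after the target day", chooses among several readings inside one window. The fill rule applies when the visit value is missing. They address different cases.
- **That every endpoint has three rules.** Only viral load could be counted that way. Saturation and counts have two each, because exclusion and non-imputation agree.
- **That the results will be falsely precise.** The documents give no variances and no precision was calculated.

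**Conclusion.** The inconsistency is established from the text alone. SAP 5.3 contradicts the stated rules for oxygen saturation, medical visits and hospital/ICU days, and nothing says which prevails. For viral load, both 5.3 and Appendix 1 substitute values that the MMRM does not need.

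The bias is conditional. It arises only if LOCF or the fill rule is actually applied. LOCF then understates each arm's decline while load is falling, and the between-arm error can go either way. On the assumed curve, with equal missingness of 5% to 18%, the difference moves by 0.02 to 0.14 log10 at Day 5 and by 0.03 to 0.11 at Day 14. These sizes rest on an assumed curve and borrowed discontinuation rates, and they illustrate rather than estimate.

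For severe symptoms there is no contradiction, but LOCF is unsuitable for the windowed analyses. The SAP should be corrected before the final analysis. The point does not bear on the primary or hospitalization/death results.

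**What to change.** - Delete the blanket LOCF sentence in SAP 5.3 and state that endpoint-specific rules prevail.
- Viral load: fit the MMRM to observed in-window values and the ANCOVA to observed Day 5 values. Keep any fill rule only as a labelled sensitivity analysis.
- Oxygen saturation: exclude missing values, as 6.2.11 already says.
- Counts: do not impute. Use the days-of-collection offset for medical visits.
- Any-severe analyses for Days 2 to 6 and Days 7 to 28: use only diary days observed within the window, and remove LOCF from those Appendix 1 rows.
- Add one line each for Week 24 death and progression to worsening, because their Appendix 1 rows name no rule for missing post-baseline data once the general sentence is gone.

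The cost is SAP wording and slightly fewer filled values. Sample size, power, and the primary and hospitalization/death analyses do not change.
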